- All subjects will be no more than 1 year post-injury, and will be symptomatic at enrollment (i.e. all subjects will exhibit evidence of ongoing posttraumatic amnesia via the Galveston Orientation Amnesia test (GOAT), OR score at least 1.5 SD below the mean for completion time on Part B of the Trail Making Test, OR score at least 1.5 SD below the mean on either the Learning and Memory short form of the Traumatic Brain Injury Quality of Life (TBI-QOL) scale or the Ruff Neurobehavioral Inventory (RNBI) Postmorbid Cognitive Domain scale.
- Agreement to undergo no changes in concomitant medications (including dietary supplements) or therapeutic interventions during the first 12 weeks of the study (that is, the 12 weeks of dosing with study drug), except where medically indicated. Intact enteral route
- English-speaking (since not all of the outcome metrics are normed outside of the English language)
- Patient can be on seizure medication.

Exclusion criteria:

- Patients taking acetylcholinesterase inhibitors and other cholinergic and anticholinergic drugs (e.g., tacrine, physostigmine, velnacrine, donepezil, rivastigmine, metrifonate) and CYP1A inducing/inhibiting drugs (ex. ciprofloxacin, enoxacin, fluvoxamine, methoxsalen, mexiletine, oral contraceptives, phenylpropanolamine, thiabendazole, zileuton, acyclovir, allopurinol, caffeine, cimetidine, daidzein, disulfiram, Echinacea, famotidine, norfloxacin, propafenone, terbinafine, ticlopidine, verapamil, montelukast, phenytoin, moricizine, phenobarbital).
- Evidence of more than 1 seizure in the past 4 weeks prior to enrollment: Patients may not be enrolled if there is evidence of more than one seizure (clinical or electrographic, but not including epileptiform or other irritative discharges) during the 4 weeks prior to enrollment.
- Premorbid history of epilepsy with seizure frequency >1 per month: Patients with a history of idiopathic epilepsy may not be enrolled if their seizure frequency was > 1 per month in the 3 months prior to injury. If pre-injury seizure frequency was < 1 per month but there is documented evidence that post-injury seizure frequency is > 1 per month or there is documented evidence of an increase in the severity or duration of a single seizure relative to the premorbid history, the patient must be excluded.

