- Evidence of premorbid major CNS disorder, developmental disorder, psychiatric disorder or substance abuse: Prior to sustaining TBI, patient was diagnosed and/or treated for a major neurologic condition, pervasive developmental disorder (e.g., mental retardation, autism), psychiatric disorder or substance abuse that continued to produce functional disability up to the time of injury. This would be demonstrated by active treatment, hospitalization, and/or documentation of active withdrawal within the 12-month period prior to enrollment. The PI will determine if the patient was a chronic substance user or simply had an overindulgence that was not maintained. If in the judgement of the PI and/or the study physician the patient exhibits no present evidence of substance withdrawal and has demonstrated a commitment to substance abstinence, the patient can be enrolled.
- Individuals with disorders of consciousness, as defined at the time of screening of having vegetative and/or minimally conscious state, will not be enrolled. However, these patients may be followed until they meet eligibility criteria
- Pregnancy, as determined by serum hCG testing before randomization
- Breast feeding females
- Significant hematologic, renal or hepatic dysfunction [Hepatic/renal dysfunction is generally identified as lab results > two times the upper limits of normal (ULN), and hematologic dysfunction is determined by clinically significant abnormal lab results], on baseline laboratory examination.
- Slow heart rate (bradycardia) or other heart conditions related to rate
- History of peptic ulcer disease
- History of asthma or emphysema as exemplified by active treatment with consistent use of disease modifying drugs within the 12-month period prior to enrollment
- History of GI/urinary tract blockages (i.e. ileus, IBS)
- History of glaucoma
- Current smoker (have smoked within 1 week of enrollment).

VII. SUBJECT ENROLLMENT

Potential subjects will be identified by the following sources:

- 1. Attending physicians may refer their TBI patients to the study. We will provide physicians with study information sheets and flyers.
- 2. Medical record review by physician on clinical treating team of inpatients in Spaulding Rehabilitation Network facilities (Boston/Cambridge). If the patient is found to be eligible based upon this search, we will contact the primary rehabilitation physician to approach the patient and/or family about participation.

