- British Columbia Post Concussion Scale
- Eye Tracking baseline measures

Study Visit Timeline:

All study visits for inpatients and outpatients will take place in-person at Spaulding. During the course of this study, the subjects will be assessed at predetermined time points. These time points are: Screening/Baseline, Week 6, Week 12, Week 13, Week 24 and Week 52. In the table below, the study visits and assessments are outlined.

As we are investigating patients with Traumatic Brain Injury, there may be instances where the study timeline will need to be adjusted. This may occur if the patient is transferred during his/her hospital stay through clinical treatment, or during follow-up scheduling. Therefore, we will employ a window of +/- 2 weeks to complete the study visits, in order to accommodate for scheduling issues and changes in the subject's care.

Study Visit Summary:

Table 1 provides a summary of the study visits and study-related activities.

Table 1: Study Visit Summary

			Admin	A Dose istration riod			
	Screening	Baseline	6 Wks	12 Wks	13 Wks	24 Wks	52 Wks
History and Physical							
Baseline Symptom Checklist	X	X	X	X	X	X	X
Pregnancy Test (Serum hCG)	X	-	-	-	-	-	-
Medical History Review	X	ı	-	-	-	-	-
TMS Screening Checklist	X	-	-	-	-	-	-
Laboratory Data (renal and liver function, hematology) including a general chemistry 6 panel at baseline	X	1	X	X	X	-	-
ECG	X	-	X	X	X	-	-
Physical Exam (to include vital signs)	X	-	X	X			
Neurocognitive							
GOAT	X	-	X	X	-	X	X
Trail Making Test A&B	X	-	X	X	-	X	X
TBI Quality of Life	X	X	X	X	ı	X	X
Ruff Neurobehavioral Inventory	X	X	X	X	-	X	X
CVLT-II	-	X	X	X	-	X	X
Brief Pain Inventory	-	X	X	X	-	X	X
Suicidality Scale	-	X	X	X	X	X	X
Beck Depression Inventory	-	X	X	X	-	X	X
British Columbia Post-	_	X					
Concussion Scale			X	X	-	X	X
Neurophysiologic							
Eye Tracking (Pupil Activation)	-	X	X	X	-	X	X
P50/P300 (EEG)	-	X	X	X	-	X	X
SAI (TMS)	-	X	X	X	-	X	X
TMS Adverse Effects Checklist	-	X	X	X	-	X	X
Concomitant Safety							
Monitoring							
Drug Side Effects	Weekly			X	-	-	
Seizure Log	Weekly			X	-	-	
Medication Log (for all medications)	Weekly -			-	-		
Adverse Event Monitoring	Ongoing Monitoring						

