On a weekly basis during the 12-week active treatment period, study staff will record medication changes that have occurred since the previous week. For inpatient subjects, study staff will conduct a structured chart review and speak with the treating physician/nursing staff to identify any medication changes. For outpatient subjects, medication monitoring will be conducted through weekly phone calls. In addition to recording medication changes that have occurred over the last week, changes in baseline symptoms, side effects from Huperzine-A, adverse events and episodes of seizure activity that may have occurred in the intervening week will also be recorded. Approximately every three months after the 12-week active treatment phase (i.e., week 24, week 36, week 52), subjects will be monitored for the occurrence of any new *serious* adverse events as well as any unresolved/unstable AEs that may have occurred during the 12-week treatment period. Subjects will be instructed to call the Study Coordinator if a serious adverse event occurs between scheduled follow-ups. Serious adverse events will be reported immediately, in accordance with DSMB and IRB policies.

Drug Administration and Dosing:

Within 7 days of completion of the baseline assessment, subjects will receive the initial dose of the study drug (Huperzine A or placebo). The study drug will be prepared and stored by a third-party vendor and will be shipped to the Spaulding pharmacy. Due to changes in Massachusetts State Laws compounding pharmacies are now required to prepare and label the study drug for each individual subject. The shelf life of the study drug has been reduced from one year to six months. The study drug will be couriered to SRH hopefully, within 24 hours of receiving the prescription. Thus, the window between randomization and first dose of study drug has been increased to seven days. The randomization list will be maintained by a Spaulding pharmacist with no access to subjects or study data. Please see Appendix I for more detailed drug administration guidelines. For inpatient subjects, the study drug will be administered by nursing staff. For outpatients, instructions will be given to the subject and/or caretaker on how to continue the dosage schedule. Weekly phone calls will be made to ensure compliance.

Dose Titration:

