Subjects/surrogates will be contacted by the study coordinator two weeks before each scheduled follow-up visit to arrange an in-person visit at Spaulding. Follow-up visits will be conducted at 6, 12, 13, 24, and 52 weeks. There will be a +/- 2-week window to complete these milestone visits to accommodate for scheduling issues. Actual dates for each visit will be recorded to ensure that the follow up visits are within the appropriate time window. In addition, we will conduct a telephone call to the subject at week 13 (one week after drug has stopped) as a safety assessment. If it is not possible to complete an in-person assessment, follow-up activities involving symptom

reporting, adverse events and medication changes will be conducted by telephone.

Inpatient-Outpatient and Acute Care Transition Procedures:

As part of this study focuses on Traumatic Brain Injury in an inpatient population, there may be subjects who are transferred from Spaulding Rehabilitation Network (SRN) inpatient to other outpatient sites (either inside or outside SRN), to acute care based on clinical treatment needs, or home. In these cases, we will follow our subjects with an intent-to-treat procedure as outlined below.

- 1. In all cases of discharge or transfer (prior to 12 weeks) we will attempt to continue the subject's dosage schedule of the investigational drug. For all subjects, regardless of whether dosing continued for the full 12 weeks, we will attempt to follow up with these subjects for follow-up assessments. Subjects who do not return for any follow-up assessments will be considered lost to follow up.
 - a. Upon discharge, instructions will be given to the subject and/or caretaker on how to continue the dosage schedule. Study staff will follow up with all monitoring procedures (as outlined in the study visit table) via weekly phone calls.
- 2. In addition, if the subject transfers to acute care:
 - a. We will attempt to continue the subject's dosage schedule as outlined above.
 - b. If this is not possible, there will be a **1 week** window during which the treatment schedule will be deferred to accommodate for appropriate acute clinical care during this time; that is, study drug may be stopped for up to 1 week, and then restarted. This restart may only happen once per patient during the trial.

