Adverse events will be collected from the start of Huperzine A treatment through the end of study participation. During the 12 weeks of study drug, all adverse events will be collected. However, after study drug dosing is complete, we will only collect information on serious and/or unresolved/unstable adverse events that are clinically meaningful. All adverse events regardless of attribution to Huperzine A will be collected and recorded, using standard adverse event forms. All applicable local regulatory requirements related to the reporting of serious adverse events to regulatory authorities and the IRB will be followed during this study. Serious adverse events will be promptly reported to the IRB. The issue of placing the study on hold will be raised by the investigators with our local IRB if any serious adverse events occur.

Importantly, a data safety monitoring board (DSMB) will be established for the study, and will be comprised of a physiatrist (rehabilitation physician) with expertise in traumatic brain injury rehabilitation, a neuropsychologist with expertise in cognitive rehabilitation, and a biostatistician with expertise in clinical trials. This DSMB will meet after 50% of the subjects complete the study, and will meet again after 20 subjects have completed the study. The DSMB will be un-blinded in their assessment of AEs and we will adopt the following stopping rules:

- We will stop the study early if any patient dies, if any patient requires emergency surgery, or if any patient suffers a permanent and irreversible disability, only if the DSMB determines that this event was definitely or probably related to study drug.
- We will also stop the study if there is disproportionate incidence of serious adverse events in the active treatment arm vs. the placebo arm. Serious adverse effects will be defined as any adverse event, including a significant change in lab values, that is: (i) fatal, (ii) life-

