- Medication Log: Prior to randomization, study staff will review the results of screening tests to identify potential drop-outs; subjects identified as being at high risk for noncompliance with study drug will not be randomized. For Spaulding inpatients, nursing staff will maintain a treatment record which will be checked weekly by study staff, and transcribed onto a medication log which will include the time, date, and each dosage of Huperzine A taken. Finally, any deviation from adherence to the medicine regime will be documented. Study data will be monitored for irregularities. Any irregularities in the data will be investigated for possible deviations in adherence. We will also track the patient's other medications (not involving Huperzine) on this Log including dosing amounts and times. For community-dwelling outpatients, subjects and/or caretakers will be given a medication diary to fill out daily.
- Laboratory Data: Serum measures of renal and liver function will be obtained at baseline, 6 weeks, 12 and 13 weeks to evaluate for eligibility to participate in the study as well as any potential unexpected side effects. Hematologic data will also be obtained at baseline, 6 weeks, 12 and 13 weeks to observe for any side effects. A general chemistry panel will be completed at baseline. Clinical blood results obtained within 48 hours of the study time

points will be able to be used for evaluation thereby, reducing the number of venipunctures for the subject.

- Biomarkers: Blood samples for UCH-L1, GFAP, NF-l and Tau will be obtained at the time of enrollment, at 24 hours, 23 days, 30 days post injury and 90 days post injury. Deidentified samples will be shipped to Quanterix Corporation for analysis after processing by the SRH clinical lab. After analysis Quanterix Corporation will return the samples to the Spaulding Rehabilitation Network Research Institute.

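### Optional safety improvement: pregnancy is an exclusion, but hCG is scheduled only at Screening; consider repeating it before first dose, at Week 6 and at the end of dosing

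*Combined protocol and SAP*

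**What the plan says.** The exclusion criteria in Section VI of the combined protocol and SAP list "Pregnancy, as determined by serum hCG testing before randomization"; breast feeding is a separate exclusion. Section VIII, Screening and Baseline Assessments, places the serum hCG among the screening laboratory studies. In Table 1 the row "Pregnancy Test (Serum hCG") has a cross at Screening and a dash at Baseline and at Weeks 6, 12, 13, 24 and 52.

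Males and females aged 18 to 65 may enrol, as inpatients or outpatients. Section VIII, Drug Administration and Dosing, says that "the window between randomization and first dose of study drug has been increased to seven days". Dose Titration and Table 2 then set five four-day steps followed by 64 days at 300 micrograms twice daily.

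Other laboratory safety checks are repeated. Section XII, Laboratory Data, says: "Serum measures of renal and liver function will be obtained at baseline, 6 weeks, 12 and 13 weeks". Hematology follows the same schedule. The section lets routine results stand in for study blood ("Clinical blood results obtained within 48 hours of the study time" points). Section VIII, Follow-up Assessments, provides a telephone fallback: "If it is not possible to complete an in-person assessment, follow-up activities involving symptom" reports, adverse events and medication changes are then done by telephone.

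**The concern.** The plan treats pregnancy as a reason not to give the drug, but checks for it once, before a 12-week exposure. A woman who conceives after that check, or shortly before it, could pass through titration and stay on the full dose with no scheduled test to prompt stopping.

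Symptoms may not fill the gap. Section XI lists nausea, vomiting, loss of appetite and increased urine among the side effects of Huperzine A. As a matter of general clinical knowledge, these overlap with early pregnancy. They could be recorded as drug effects, or handled under the intolerance rule in Section VIII, which steps the dose down for 7 days and then raises it again.

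Follow-up is also at stake. Section XI says that "after study drug dosing is complete, we will only collect information on serious and/or unresolved/unstable adverse events that are clinically meaningful". A congenital anomaly counts as a serious event there, but an uncomplicated exposed pregnancy that nobody knew of during dosing might never be recorded for follow-up.

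**Working it through.** **Inputs**

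- Dosing: five steps of 4 days, then 64 days (Section VIII, Dose Titration and Table 2).
- Randomization to first dose: 7 days by one sentence of Drug Administration and Dosing. The same section also allows 7 days from baseline to first dose, and Screening and Baseline Assessments allows 7 days from randomization to baseline.
- Screening to randomization: no figure given.
- Visit window: plus or minus 2 weeks (Section VIII, Study Visit Timeline).
- Week 6 is taken as day 42 of dosing. This is an assumption, because the starting point of the visit clock is not fixed in the text.

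**1. Length of dosing.** 5 × 4 + 64 = 84 days = 12 weeks. This reproduces the plan's own figure.

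**2. Scheduled hCG after Screening.** None at any of the 6 later visits, so none during the 84 days.

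**3. Age of the only test at the end of dosing.**

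- With the single seven-day window fully used: 7 + 84 = 91 days.
- With both separate seven-day windows fully used: 7 + 7 + 84 = 98 days.

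In each case the Screening-to-randomization gap is extra. Section VIII also allows one deferral of up to a week during acute care. It is not counted here, because the text does not say whether it moves the end of dosing.

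**4. Dosing days that a positive Week 6 test could still prevent.**

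- Nominal: 84 − 42 = 42.
- Visit two weeks early (day 28): 84 − 28 = 56.
- Visit two weeks late (day 56): 84 − 56 = 28.

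**5. Longest stretch of dosing before a scheduled test.** It falls from 84 days to 42 nominally. It is at most 56 when the Week 6 visit sits at either end of its window.

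**6. What Week 6 leaves uncovered.** Titration takes 5 × 4 = 20 days, so the full dose starts on day 21. A conception too recent for Screening would be exposed for 42 days before a Week 6 test (28 to 56 with the window). Of these, 42 − 20 = 22 days would be at 600 micrograms a day (28 − 20 = 8 to 56 − 20 = 36). Only a repeat test close to first dose addresses this case.

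**7. Number of added assays.** Three per woman of childbearing potential. The documents do not say how many such women there will be. The ceiling is 3 × 30 = 90 if all 30 participants qualified; if half did (an illustration), 3 × 15 = 45.

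**The case against.** The plan is consistent with itself. Section VI, the screening list and Table 1 all describe one test before randomization, so a reader who inferred a contradiction would be wrong.

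There are also other routes to discovery. Staff contact or review every participant weekly during dosing, and physical examinations are scheduled at Weeks 6 and 12. Reports come from authorized representatives, caregivers, nurses and treating physicians as well as from the participant. All adverse events are collected during dosing whatever their cause, and the DSMB reviews unexpected problems that put participants or other people at risk. In a trial of 30, an added test will most likely find nobody. All of this is fair and lowers the priority. It does not close the gap, because none of these routes is a pregnancy test, and they depend partly on symptoms that the drug itself may cause.

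The remedy has limits too. A Week 6 test alone comes late for a conception missed at Screening. A test at the end of dosing prevents little or no exposure, except that a Week 12 visit held two weeks early would still leave up to 14 dosing days.

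A stronger reading is tempting. The excluded drugs include oral contraceptives ("fluvoxamine, methoxsalen, mexiletine, oral contraceptives, phenylpropanolamine"), and the supplied text states no contraception criterion, so one might infer that women are left unprotected or unadvised. The documents do not support that. The consent pages were removed and Appendix I was not supplied, and either may cover contraception and pregnancy reporting.

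**Conclusion.** The point stands as an optional, low-cost safety improvement: one scheduled hCG, none in 84 days of dosing, and a result at least 91 to 98 days old at the end if the pre-dose windows are fully used. The estimate of 42 preventable dosing days (28 to 56) rests on counting Week 6 from first dose.

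A reader might go further and infer an expected number of exposed pregnancies, or of harmed fetuses. Neither can be computed. The documents give no count of women of childbearing potential, no conception rate and no reproductive-toxicity data. The most that can be said is that the number would be small. The point does not touch the primary analysis, the sample size or any error rate.

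**What to change.** For women of childbearing potential, amend Table 1 as follows:

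1. **Just before first dose:** repeat hCG, to cover conceptions too recent for Screening. This may need its own sample. Table 1, as read here, shows no laboratory draw at Baseline, and the baseline blood in Section XII appears to be the eligibility draw.
2. **Week 6:** add hCG to the blood already scheduled. This is the test that can stop further exposure.
3. **End of dosing:** add hCG to the Week 12 or Week 13 draw, to identify exposed pregnancies for follow-up. Week 13 covers the last dosing days better, but Section VIII also describes a telephone call then, so name the visit at which blood will be taken.

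The sponsor and the IRB should state what a positive result triggers: stopping, reporting and follow-up to outcome.

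The cost is a protocol amendment, three assays per woman and the pre-dose sample. A separate sample will also be needed now and then, where routine results replace study blood or the visit is by telephone. An occasional woman would stop study drug.
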